1. STUDY POPULATION

1.1 Population (base)

The research population will be recruited from couples either presenting for evaluation of started fertility treatment or newly presenting with infertility to a gynaecologist or after successful pregnancy. A recruitment of 1200 male patients is proposed. Participants will be recruited from both tertiary and secondary care hospitals. Expected inclusion period is 24 months, since we expect to enrol around 50 patients per month. With a participation rate of 50%, the recruitment of 1200 males in 24 months is feasible (see 2.3 sample size calculation). Due to the existence of the NVOG Consortium 2.0 structure (Dutch Consortium for Healthcare Evaluation in Obstetrics and Gynaecology) the experience of the participating hospitals in including patients is high, most clinics have an onsite research nurse.

1.2 Inclusion criteria

In order to be eligible to participate in this study, a subject must meet all of the following criteria:

- Either: couples with failure to conceive for at least 12 months and starting with EM **or** couples starting with 1st/ 2nd/3rd cycle of IUI (with/without ovarian stimulation) **or** 1st/ 2nd/3rd cycle of IVF/ICSI
- Male with age 18-50 years
- Female partner with age 18-43 years
- Willing and able to give informed consent

Exclusion criteria

A potential subject who meets any of the following criteria will be excluded from participation in this study:

- Planned or performed diagnostic testicular biopsy (TESE) or percutaneous epididymal sperm aspiration (PESA)
- Use of donor-, cryopreserved- or electro-ejaculated semen
- Ovulation induction (OI) without IUI
- IVF for an absolute tubal factor
- Embryo-transfers after cryopreservation
- Embryo-transfer after pre-implantation genetic diagnosis
- Known endocrine abnormalities related to infertility, or use of fertility enhancing drugs
- Known genetic abnormalities related to infertility
- Known urological abnormality such as a varicocele or bilateral cryptorchism
- Use of other vitamin supplements

1.3 Sample size calculation

The overall success rate (number of ongoing pregnancies, not specified per cycle number) in IVF and ICSI in the Netherlands was respectively 19.8% and 21.5% per cycle in 2015.(23) The cumulative number of ongoing pregnancies in IUI is estimated to be around 5 to 13% per cycle, around 18% after three cycles and 20-30% after six cycles. (24-26) Based on our Radboudumc data, the ongoing pregnancy rate in EM is estimated around 20% after 6 months.

A Cochrane review ‘antioxidants for male subfertility’ estimated the increase in clinical pregnancy rates after use of antioxidants with an Odds Ratio (OR) of 3.43 (95% CI 1.92 to 6.11, $P < 0.0001$, 7 RCTs, 522 men, $I^2 = 0\%$, low quality evidence). (27) However, this concerns low quality evidence, and the included population in this Cochrane review was couples with male factor subfertility, whereas in our study we also include couples with unexplained infertility. Therefore, we assumed a more conservative OR of 1.5. Assuming a 20% ongoing pregnancy rate in the placebo group, this reflects in an expected pregnancy rate of 27.3% in the Impryl® group

The study is designed as a superiority study. Based on the above mentioned data, we expect a 7.3% increase in ongoing pregnancy number when men are treated with Impryl® compared to placebo. However, after randomization patients can directly start with both intervention and achieving a pregnancy, either spontaneously or with fertility treatment. In these first months the effect of the intervention is expected to be suboptimal due to the duration of the spermatogenesis (72 days before whole renewal). Therefore we adjusted the expected increase of 7.3% to a more realistic effect of 6.5%. We assume an equal increase in all fertility groups (meaning EM, IUI and IVF/ICSI) from 20% to 26.5%.

The ratio between the 3 fertility treatment groups (EM 1: IUI 3: IVF/ICSI 2) is based on the number of new patients treated at Radboudumc and the sites each year. To test the effect of Impryl on the probability of ongoing pregnancy, a sample size of 600 men per treatment group (1200 in total) is needed, assuming differences in ongoing pregnancy rates of 6.5% and an expected ongoing pregnancy rate of 20% in the placebo group, with a two-sided alpha of 5% and a beta of 24% (i.e. 76% power). As we expect the number of participants lost to follow up to be minimal. We will allocate 600 patients in both intervention and control arm. Figure 1 shows the distribution of the number of participants for the 3 different types of fertility treatment (EM, IUI and IVF/ICSI).

2. TREATMENT OF SUBJECTS

For the purpose of this study subjects will either be treated with a food supplement (Impryl®) 1 tablet once a day or with a placebo 1 tablet once a day, both for a duration of maximum 6 months. Use of the food supplement or placebo will be stopped earlier when pregnancy is achieved.

2.1 Investigational product/intervention

Impryl® tablets will be produced by Labomar SRL who will also produce an identical looking placebo tablet. Patients start directly with study medication for a total duration of maximum 6 months.

2.2 Use of co-intervention

All couples will receive our standard care for infertility according to the guidelines of the Dutch Society of Obstetrics and Gynaecology. After diagnostic work up couples will either start with EM (6 months), IUI, IVF or ICSI. Participants will take study supplement for a maximum of 6 months, even if the fertility intervention (6 x IUI or 1 x IVF/ICSI cycles) is not completed. Co-treatment with other vitamins or supplements is prohibited. If vitamins or supplements are already used by men, a wash-out period of 3 months is recommended. Patients using other supplements will be excluded or reported as protocol violation. If after randomization it appears that a patient still uses other supplements (reported in the online questionnaire), they will be telephonically contacted and asked to stop use of other supplements. After this stop, there is a wash-out period of 72 days (duration of spermatogenesis). If no pregnancy occurs within this wash-out period the patient and data can still be included.

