5.1.3 Other study parameters

Baseline parameters are age, length, weight, ethnicity, alcohol/drugs/nicotine use, use of vitamins/steroids or other supplements, diet specifics (normal, vegetarian, vegan, gluten-free, dairy free, other), medication use, activities that cause increased scrotal temperature such as often visiting a sauna, taking a hot bath or race cycling, general health, operations or trauma in genital area, exposure to toxins in environment, conception of previous children, duration of infertility and type of diagnosis of infertility. Furthermore the age and parity of the female partner has to be documented, as well as the occurrence of endometriosis or anovulation.

Furthermore, when IVF/ICSI is performed, the amount of embryos transferred will be reported, either a single-embryo transfer (SET) or double-embryo transfer (DET).

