5.3 Study procedures

Couples matching the inclusion criteria will be asked to participate in the trial. If after diagnostic work up the diagnosis infertility for the couple remains, both are asked for informed consent. After signing informed consent, the male patient will be randomised and allocated to Impryl® or placebo (double blinded).

Medication

Patients can directly start using the food supplement or placebo. Impryl® or placebo will be taken for a total duration of 6 months and will be directly stopped after having a positive pregnancy test.

Baseline characteristics

Patients are asked to report on these characteristics by a short questionnaire. Patients will receive an automatic email invitation directly after randomisation and are asked to provide this information online in the Castor database system

Lifestyle and outcome characteristics

Patients will be asked once every month to report on occurrence of pregnancy (with date of positive test), changes in weight and diet, changes in habit of smoking and drug or alcohol use, occurrence of fever and change in activities increasing scrotal temperature (hot baths, sauna, race cycling). Furthermore patients are instructed about taking note of the total amount of consumed study medication (used boxes and tablets). There is a question about the occurrence of adverse events. Patients will receive an automatic email and are asked to provide this information online in the Castor database system. When a pregnancy has been reached during the 6 months use of study medication the monthly questionnaires will be stopped, because there is no more necessity to record on lifestyle changes and treatment compliance.

Semen analysis

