5.5 Follow-up of subjects withdrawn from treatment

As the statistical analysis is planned according to intention to treat principle, patients that violate the study protocol will be analysed in the group that they were allocated to. All patients will receive full follow-up.

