7. STATISTICAL ANALYSIS

All data will be analyzed on an intention-to-treat basis. Data of patients who are lost to follow-up, will be included in their randomised group

will be included in their randomized group:

- Patients who are lost to follow-up during the treatment period are considered not to have achieved a pregnancy.
- Patients, who are lost to follow-up right after achieving a pregnancy of less than 8 weeks of gestation, are considered not to have achieved an ongoing pregnancy
- Patients, who are lost to follow-up right after achieving a pregnancy of 8 or more weeks of gestation, are considered to have achieved an ongoing pregnancy.

In addition, a per-protocol analysis will be performed for the primary outcome and the secondary outcomes overall pregnancy number, time to pregnancy, number of miscarriages and live birth rate.

Descriptive statistics will be calculated to check for major dissimilarities between study groups with respect to baseline information. Baseline data will be described quantitatively. For continuous variables, we will examine the distribution of the observations, and if normally distributed we will summarise them as means with standard deviations (SDs). If they are not normally distributed, then medians and inter-quartile ranges (IQRs) will be reported. For dichotomous data, we will provide counts and proportions.

The primary outcome variable 'ongoing pregnancy' will be assessed as follows. The ongoing pregnancy percentages as observed in the trial will be presented for both treatment arms, overall, and separately for the three strata (i.e. EM, IUI, IVF/ICSI). In order to adjust for possible imbalances between the treatment groups, the pregnancy percentages and differences in pregnancy percentages between the experimental and control group, and the corresponding 95% confidence intervals will be estimated using a fixed effects binomial model with an identity link, including intervention, fertility treatment, centre and female age (centered). If this model does not converge, a logit link will be used.

Time to ongoing pregnancy will be evaluated by the Kaplan-Meier approach; differences between the two arms will be tested with the log-rank test. Similar analyses will be conducted per stratum (EM, IUI or IVF/ICSI). The other secondary outcomes (overall pregnancy number, number of miscarriages, live birth rate, fertilization rate, embryo-utilization rate) will be evaluated similarly to the primary outcome. Changes in semen

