analysis, leading to different fertility treatment categorisation, will be first calculated with descriptive statistics, with the following codes:

- 0: if there is no change in treatment category
- 1: if there is 1 category change (i.e. from IUI to EM), or -1 if it goes from less severe to severe (i.e. IUI to IVF)
- 2: if there are 2 category changes (i.e. from IVF to EM)

The changes will be summarized with descriptive statistics (mean, SD, median, range) and frequency tables per treatment and stratum. Further, the difference between the experimental and control group will be assessed with a fixed effects linear model, adjusted for centre and stratum.

Furthermore, adverse events will be summarized. Sensitivity analyses will be performed to evaluate possible effects in case of protocol amendments.

The per-protocol population will consist of all randomised patients without any major deviation from the protocol. A major protocol deviation is defined as

- Use of other nutritional supplements without a wash-out period
- Intake of study medication of less than 75% of the prescribed amount

Participants will be asked by automatic email to report in Castor their actual compliance to the intervention by taking note of total amount of consumed study medication (used boxes and tablets). Patients will also be asked to report about major changes of their lifestyle occurring during the study period (see page 22).

The results will be extracted from Castor. If there are missing data this will be mentioned along with the reason.

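### Section 2.2 makes keeping a randomised supplement user's data depend on no pregnancy in a 72-day wash-out; it names no analysis set and, on its likelier reading, selects the per-protocol set on outcome

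*Combined protocol and SAP*

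**What the plan says.** Section 1.2 lists "Use of other vitamin supplements" as an exclusion criterion. Section 2.2 covers men whose use comes to light after randomisation, through the online questionnaire. They are telephoned and asked to stop, and a 72-day wash-out follows. Then: "If no pregnancy occurs within this wash-out period the patient and data can still be included". The same section offers two ways of handling supplement users, exclusion or recording a violation, and gives no rule for choosing between them.

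The analysis sections carry no such condition. Section 5.5 says that "patients that violate the study protocol will be analysed in the group that they were allocated to", and section 7 opens with "All data will be analyzed on an intention-to-treat basis". Section 7 adds that "a per-protocol analysis will be performed for the primary outcome and the secondary outcomes overall pregnancy number, time to pregnancy", and goes on to miscarriages and live birth. One of its two major deviations that remove a man from the per-protocol set is "Use of other nutritional supplements without a wash-out period".

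The primary endpoint (section 5.1.1) counts ongoing pregnancies conceived from randomisation through month 6. Section 5.2 places the definition of protocol violators before unblinding.

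**The concern.** A condition for keeping a man and his data has meaning only if failing it changes something, and here the condition is that no pregnancy occurred. The 72 days can lie inside the primary window, so a conception in them can be a primary event. Of two men flagged for the same supplement use, the one whose partner conceives on day 30 would leave and the one whose partner does not would stay.

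Whether a couple is counted should not depend on whether it conceived. The per-protocol analyses repeat the primary outcome and several secondary ones, and readers will take them as support for the main result. In the time-to-pregnancy analysis, flagged men who are kept would have their earliest possible event pushed back, because any couple with a conception inside the wash-out is gone.

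**Working it through.** **Design as stated (section 1.3).** 20% vs 26.5%, two-sided alpha 5%, 600 per arm. The pooled two-proportion formula gives 76.0% power, as stated. The odds ratio is (0.265/0.735)/(0.20/0.80) = 1.44. No figure in the plan is disputed.

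**Assumptions not in the documents.**
- A share q of men in each arm is flagged (5-20%).
- They stop other supplements close to randomisation, so the wash-out starts at about day 0.
- Placebo conceptions are even over 6 months, so the window holds f = 72/182.6 = 39.4% of them.
- Flagged couples who conceive in the window are dropped. Only conceptions that become ongoing pregnancies are modelled.
- The set's rates are otherwise 20% and 26.5%.

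**Formula.** Let w be the probability of such a conception in the window. The counted rate is (p - q·w)/(1 - q·w).

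Placebo: w = 0.20 × 0.394 = 0.0789. With the full effect from day 1, the Impryl value is 0.265 × 0.394 = 0.1045. Section 1.3 expects a suboptimal effect in the first months, so the early excess is scaled by k: w = 0.0789 + k × (0.1045 - 0.0789).

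**Results at q = 20%, equal in both arms.**

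| Early effect k | Placebo | Impryl | Difference (points) | Odds ratio |
|---|---|---|---|---|
| 1 (full) | 18.72% | 24.93% | 6.21 | 1.44 |
| 0.5 | 18.72% | 25.13% | 6.41 | 1.46 |
| 0.25 | 18.72% | 25.22% | 6.51 | 1.46 |
| 0 (none in 72 days) | 18.72% | 25.32% | 6.60 | 1.47 |

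Worked case, k = 0: placebo (0.20 - 0.0158)/(1 - 0.0158) = 18.72%; Impryl (0.265 - 0.0158)/(1 - 0.0158) = 25.32%.

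Among flagged men alone (q = 1), the rates are 13.15% vs 17.93% (4.77 points, unrounded) with full early effect and 13.15% vs 20.21% (7.06 points) with none.

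**Smaller shares, full early effect.** q = 5%: 6.43 points. q = 10%: 6.36 points.

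**Other window shares, q = 20%.** With f = 30%, the difference is 6.28 points (full early effect) or 25.61% - 19.03% = 6.58 (none). With f = 50%, it is 6.13 or 25.00% - 18.37% = 6.63.

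**Constant conception rate instead of even conceptions, full effect, q = 20%.** w = 1 - 0.8^(72/182.5) = 8.43% and 1 - 0.735^(72/182.5) = 11.44%. The rates are 18.63% vs 24.78%, a difference of 6.15 points.

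**Unequal flagging, no true effect (20% in both arms).** q = 10% gives 19.36% and q = 20% gives 18.72%: about 0.65 spurious points (unrounded rates) in favour of the arm with fewer flagged men.

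**Power, only if the rule reached the primary analysis, q = 20%.** 73.3% with full early effect; about 78% with none.

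**The case against.** The strongest reply is that nothing in the text removes anyone. Section 2.2 does not say that couples who conceive are dropped, and its option of recording a violation leads directly to analysis as allocated under section 5.5. Section 7's deviation mentions a wash-out but not pregnancy. Much of this stands: the converse is inferred, and what the documents show for certain is an unresolved text. But section 2.2 speaks of the data as well as the patient. Section 7's deviation turns on the wash-out and does not say how a conception during it is classified. Whoever fixes the violators must therefore decide that case, and section 2.2 points them to pregnancy.

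Three stronger readings are tempting, and the documents do not support them.

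- A reader might infer that the primary analysis departs from intention to treat. Sections 5.5 and 7 are unconditional, and the wash-out wording in section 7 ties the rule to the per-protocol set.
- A reader might infer that equal flagging must dilute the effect and leave the odds ratio unchanged. That holds only if the full effect is present from day 1, which section 1.3 denies. With a weak early effect the difference is unchanged or slightly larger.
- A reader might infer that the rule creates an event-free first 72 days peculiar to flagged men. Section 5.1.2 dates the event at ultrasound-confirmed ongoing pregnancy, at 10-12 weeks of gestation, so almost no couple has an event that early. The earliest event for flagged men is delayed, no more.

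It is also fair that the size is trivial, that 5-20% is an assumption, and that blinding makes unequal flagging unlikely.

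**Conclusion.** The point holds as an unreconciled rule which, on its evident converse, lets pregnancy decide who is counted. Section 2.2 should not be left to be interpreted when violators are defined. On the likelier reading the primary intention-to-treat result is untouched and the per-protocol analyses are affected.

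The size is small. With 20% flagged equally and 39% of placebo conceptions in the window, the 6.5-point difference becomes 6.2 to 6.6 points and the odds ratio lies between 1.44 and 1.47, depending on how early the effect begins. The other window shares and the constant-rate version keep the difference between 6.1 and 6.6. The direction cannot be stated in advance. All of this rests on the assumed flagging rate and on other supplements being stopped near randomisation. The case for change is the principle and the low cost, not the magnitude.

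**What to change.** Reconcile sections 2.2, 5.5 and 7 as follows.

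1. Remove the pregnancy condition from section 2.2 as an analysis rule, and say how its two handling options map to the analysis sets. Clinical wash-out advice is left to the investigators.
2. State that every randomised couple, and every pregnancy in the primary window, stays in the intention-to-treat analysis whatever the supplement use.
3. Define the per-protocol supplement deviation before unblinding, from reported supplement use alone. Men with the same reported use are then all in or all out, whether or not a pregnancy followed.
4. Use only reports up to a time point common to couples who did and did not conceive, because the monthly questionnaires stop at pregnancy and later use is seen only in those who have not conceived.

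One option for item 4 is the baseline questionnaire. Section 5.1.3 lists "use of vitamins/steroids or other supplements" among the baseline items, and section 5.3 says "Patients will receive an automatic email invitation directly after randomisation". Its drawback, which the text should state, is that it misses later use.

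The cost is two or three sentences. The monthly items listed in section 5.3 do not name other supplements, and no section says that start or stop dates are recorded. The sponsor should confirm whether use and stop date are logged at the telephone contact. If they are not, a definition based on the baseline report needs no added data item.

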2.3 Escape medication

Not applicable

3. INVESTIGATIONAL PRODUCT

Impryl® is a food supplement and is therefore not considered an investigational medicinal product. To assess product quality, we have submitted following documents of both the food supplement and placebo: Summary of Product Characteristics (SPC), Certificates of Analysis (CoA), certificate of Good Manufacturing Practice (GMP) and ISO 9001 form (see documents D2 SPC, D2 CoA, D2 GMP Labomar SRL and D2 ISO 9001 Labomar SRL).

3.1 Name and description of investigational product(s)

Impryl®. Tablets of ovoid shape sized 20x8 mm, white color, smooth surface, weight 1300 milligram with active ingredients: microcrystalline cellulose, betaine hydrochloride, L-cysteine, mono and diglycerides of fatty acids, magnesium stearate, disilicio dioxide, zinc bisglycinate, croscarmellose sodium, niacin (nicotinamide), vitamin B6 (pyridoxine hydrochloride), vitamin B2 (riboflavin), folic acid [(6S) -5-methyltetrahydrofolate acid, glucosamine salt], vitamin B12 (cobalamin).

Placebo tablet of identical appearance produced by Labomar SRL.

List of ingredients of placebo (composition):

| E num. | Common name | Grams per dose |
|--------|--------------------------------|----------------|
| E 460 | Cellulose | 0,852 |
| E 341 | Calcium phosphates | 0,300 |
| E 172 | Iron oxides | 0,024 |
| E 551 | Silicon dioxide | 0,012 |
| E 470b | Magnesium salts of fatty acids | 0,012 |

3.2 Summary of findings from (non-) clinical studies

To date no (non-)clinical research with a primary focus on increasing the ongoing pregnancy number by Impryl® has been performed. There is evidence that Impryl® reduces oxidative stress and DNA damage, this is based on research performed with the previous version of the supplement (Condensyl®) in humans.(13)

